Please note that source data collected as part of routine clinical care may be used to complete CRFs as long as the window between prior data collection and operative procedures does not exceed six months. This includes previously performed POP-Q exams as well as previously collected questionnaires.

Randomization

Randomization will be assigned using RedCAP in the operating room *immediately prior* to mesh graft attachment to the vagina. Both types of sutures will be available at each site. Participants will be randomized to 2-0 GoreTex/CV4 GoreTex (depending on availability of Stitchkit) versus 2-0 PDS in blocks with block sizes of 2, 4 and 6 for each of the 5 sites. Randomization will be stratified by site.

Surgery (\leq 3 months from Baseline Visit)

Study data for the surgical procedures includes the Surgical Procedures Form and review of adverse events.

- Surgical Procedures Form
- Review of Adverse Events (if applicable)

Laparoscopic or Robotic Approach

Prior to sacral colpopexy all participants of the trial will undergo total laparoscopic hysterectomy (with or without robotic assistance) with or without bilateral salpingoophorectomy (at the discretion of the patient and surgeon).

Laparoscopic sacral colpopexy will be performed with or without robotic assistance. The configuration of the incisions is not standardized.

1. Total laparoscopic hysterectomy (with or without robotic assistance) will be performed in standard fashion and the uterus will be delivered through the vagina with no power morcellation performed. The vaginal cuff will be closed using an absorbable suture in 1 layer (suture type at the discretion of the operating surgeon). Closure of the vaginal cuff through a transvaginal approach is not allowed.
2. The same ultra-lightweight Type 1 polypropylene mesh (Upsylon, Boston Scientific) will be used for all study subjects.

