 - c) Assessment for re-intervention or re-surgery for recurrence or persistence of POP: No need for pessary use or additional surgical treatment for prolapse at any time after the initial procedure
 - d) No mesh / suture exposure
2. Assessment of participant changes in QoL, symptom bother, and sexual functioning at 1 year compared to baseline^{30,31}:
 - PFDI 20-Pelvic Floor Distress Inventory
 - PFIQ-7-Pelvic Floor Impact Questionnaire
 - PISQ-IR-Pelvic Organ Prolapse/Urinary Continence Sexual Questionnaire

3. Assessment of procedure-related or pelvic floor-related adverse outcomes in each group as classified according to the Clavien-Dindo surgical complication grading scale²⁹. Adverse events will be assessed intra-operatively, at 6 weeks, 6 months, and 1 year postoperatively.

STATISTICAL CONSIDERATIONS

Statistical Methods

Data analyses will include t-tests for continuous data, chi-square or Fisher's exact for categorical data, and multi-variable regression to assess the effects of any bivariate analyses found to have a positive relationship. Confidence intervals will be reported for continuous data and will be included in the assessment and reporting of outcomes. When the data are analyzed, both chi square and Fisher's exact analyses are performed and the appropriate test and associated p value will be used based on the proportion of samples with input less than 5% of the total population. Those with a small output will utilize Fisher's exact.

The data will be analyzed as Intent to Treat. Missing data may occur if subjects fail to return for follow up, thus we plan to over-recruit in order to account for a 20% drop-out rate. Since study participants are undergoing surgery, they are more likely to return for their follow-up visits since these are part of their standard post-operative care. This will decrease the rate of drop-outs. The fact that this is an RCT will minimize the chance of a differential drop-out rate between the groups.

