Statistical testing will be performed to determine if the incidence of mesh and suture exposure in the absorbable suture arm is non-inferior to the permanent suture arm. The null hypothesis is that the incidence of mesh and suture exposure in the absorbable suture arm will be equal to the incidence of mesh and suture exposure in the permanent suture arm.

Secondary Hypotheses

1. Statistical testing will be performed to determine if the composite success rate in the absorbable suture arm will be non-inferior to the permanent suture arm. The null hypothesis is that the success rate in the absorbable suture arm is less than or equal to the success rate in the permanent suture arm.
2. Statistical testing will be performed to determine if the symptomatic success rate in the absorbable suture arm is non-inferior to the permanent suture arm. The null hypothesis is that the success rate in the absorbable suture arm is less than or equal to the success rate in the permanent suture arm.
3. Statistical testing will be performed to determine if the AE incidences rate of the absorbable suture arm is non-inferior to the permanent suture arm. The null hypothesis is that the AE incidences rate in the absorbable suture arm is greater than or equal to the rate in the permanent suture arm.

STUDY MONITORING AND DOCUMENTATION

The Principle Investigator will monitor the study and assess the need for amendments as the study progresses. If a protocol revision is necessary for reasons including but not limited to the rights, safety or welfare of participants, or scientific integrity of the data, an amendment is required. Appropriate approvals (e.g., IRB) of the revised protocol must be obtained prior to implementation at each site.

Site Documentation

All study documents included in this protocol that will be presented to subjects will be submitted to the IRB for approval. Each site will maintain a site study binder that will include the following:

- Enrollment log of patients who have consented to be in the study (electronic version)
- Protocol Deviation Log (electronic version)
- Adverse Event Log (electronic version)
- Investigator protocol and amendments
- IRB submissions, modifications, renewals
- Data Coordinating Center monitoring correspondence
- DSMB reports
- IRB approved Informed Consent Form

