After 50% of all study subjects have presented for the 6-week post-operative check, the overall rate of mesh and suture exposure will be calculated. If this rate is >12%, the study will be terminated. A second stopping parameter will be a difference in erosion rates between the two groups of >50%.

Reporting Adverse Events

Adverse events will be recorded and reported according to criteria and timeline below. Sites will also follow local regulatory standards for AE reporting.

All AEs must be recorded on the AE CRF, entered into the site AE log, then entered into REDCap. An event number will be assigned by each site and recorded on the CRF according to the number of AEs reported per patient. Each site investigator will determine the relationship of the AE to the operative procedures, the relationship of the AE to the pelvic floor, and the severity of each reportable AE.

SAEs must be reported to the DSMB within two business days as outlined above in the Data Safety Monitoring Board section.

Reportable AEs include those determined to be related to the operative procedures or pelvic floor. AEs not related to the operative procedures or pelvic floor will not be collected. Operative procedures include the following: Hysterectomy, sacrocolpopexy, sling, anterior and posterior vaginal repairs.

Please note that underlying diseases are not reportable AEs unless there is an increase in severity or frequency during the course of the investigation. Death should not be recorded as an AE, but as an outcome of a specific SAE. If an AE has not resolved at the time of AE Form completion, save form as incomplete in REDCap until resolved. Once resolved, complete item 22 on AE form and enter into REDCap and save form as complete.

Adverse Event Definitions

Adverse Event: any untoward medical occurrence, unintended disease or injury, or any untoward clinical signs (including abnormal laboratory finding) in subjects, whether or not related to the operative procedures

Serious Adverse Event: an adverse event that:

- Led to death
- Led to serious deterioration in the health of the subject that either resulted in
 - a life-threatening illness or injury
 - a permanent impairment of a body structure or a body function
 - in-subject or prolonged hospitalization of existing hospitalization
 - medical or surgical intervention to prevent life-threatening illness or injury or permanent impairment to a body structure or a body function

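### The between-arm adverse-event comparison includes hysterectomy events that occur before the suture is allocated, which weakens secondary hypothesis 3 without biasing it

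*Combined protocol and SAP*

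**What the plan says.** **Timing of allocation.** Under Randomization: "Randomization will be assigned using RedCAP in the operating room *immediately prior* to mesh graft attachment to the vagina".

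**Order of the operation.** Under Laparoscopic or Robotic Approach: "Prior to sacral colpopexy all participants of the trial will undergo total laparoscopic hysterectomy". Closure of the vaginal cuff belongs to that hysterectomy step.

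**What the outcome covers.** Secondary Outcome Measures, item 3: "Assessment of procedure-related or pelvic floor-related adverse outcomes in each group as classified according to the Clavien-Dindo surgical complication grading scale". The same item adds: "Adverse events will be assessed intra-operatively, at 6 weeks, 6 months, and 1 year postoperatively".

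**What is reportable.** Under Reporting Adverse Events: "Reportable AEs include those determined to be related to the operative procedures or pelvic floor". The section then defines the procedures: "Operative procedures include the following: Hysterectomy, sacrocolpopexy, sling, anterior and posterior vaginal repairs".

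**What is tested.** Item 3 under Secondary Hypotheses: "Statistical testing will be performed to determine if the AE incidences rate of the absorbable suture arm is non-inferior to the permanent suture arm". Its accompanying null is that the absorbable arm's AE rate is at least as high as the permanent arm's. No margin is given.

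No section restricts the compared events to those that begin after randomisation, and none asks for earlier events to be tabulated separately. Table 1 has a single Surgery column for AE assessment.

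**The concern.** Every participant has a total hysterectomy, with cuff closure, before an arm exists for her. An injury or bleed in that part of the operation is related to a listed procedure, is assessed intra-operatively, and so enters the arm comparison. It carries no information about the suture.

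Two things follow. A real difference in the proportion of women with any AE is attenuated, because a woman with an earlier event already counts whatever happens later. Events unrelated to treatment also add sampling variation. The stake is the sensitivity of the trial's only formal comparison of AEs between the two sutures.

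**Working it through.** **Sequence.** Hysterectomy and cuff closure, then allocation, then vaginal mesh attachment. Intra-operative events from the start of mesh attachment onward follow allocation and belong in the comparison. The dissection of the vesicovaginal and rectovaginal spaces is not timed against allocation in the text.

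**Inputs from the documents** (Sample Size). 80 evaluable per arm; 200 enrolled, that is 160 / (1 − 0.20) = 200, or 100 per arm. Alpha is given as 0.1 and described as one-sided. With 10% against 1%, power 0.8 and an uncorrected chi-square, the usual formula gives 79 per arm at one-sided 0.05 (two-sided 0.10) and 57 at one-sided 0.10. The stated 80 therefore fits one-sided 0.05, and both levels are shown below. No AE rate, margin or power is stated for hypothesis 3, so there is no plan figure to reproduce for it.

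**Assumptions.** A share q of women has a qualifying event before randomisation: 3%, 5% or 10%, the same in both arms and independent of later events. Post-randomisation rates p are 30% (permanent) and 15% (absorbable). The rate means women with at least one AE; the protocol does not say whether women or events are counted.

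**Formulas.** Observed rate = q + (1 − q)p, so the observed difference = (1 − q) × 15 points. The standard error (SE) of the difference is √[(P₁(1 − P₁) + P₂(1 − P₂)) / 100], with P₁ and P₂ the observed rates. Power uses the pooled-variance normal formula with 100 per arm.

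| q | Observed rates | Difference (points) | SE (points) | Power, one-sided 0.05 | Power, one-sided 0.10 |
|---|---|---|---|---|---|
| 0 | 30.0% vs 15.0% | 15.0 | 5.81 | 82% | 90% |
| 3% | 32.1% vs 17.55% | 14.55 | 6.02 | 77% | 87% |
| 5% | 33.5% vs 19.25% | 14.25 | 6.15 | 74% | 85% |
| 10% | 37.0% vs 23.5% | 13.5 | 6.43 | 67% | 79% |

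With 80 per arm and one-sided 0.05, the sequence is 73.8%, 68.9%, 65.8% and 58.6%.

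**Direction.** Under the stated null, success means showing a lower AE rate with absorbable suture, so attenuation makes success harder. The opposite effect needs a margin and a truly worse absorbable arm. Assume a 10-point margin, post-randomisation rates of 30% (absorbable) and 20% (permanent), 100 per arm and one-sided 0.05. The true excess then equals the margin, and the observed excess is (1 − q) × 10 points. The chance of falsely declaring non-inferiority is Φ[(10 − observed excess) / SE − 1.645]:

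- q = 0: 5.0%
- q = 3%: Φ[(10 − 9.7) / 6.26 − 1.645] = 5.5%
- q = 5%: Φ[(10 − 9.5) / 6.37 − 1.645] = 5.9%
- q = 10%: Φ[(10 − 9.0) / 6.59 − 1.645] = 6.8%

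**The case against.** The strongest reply is that nothing here is biased. Events before allocation have the same expectation in both arms, the test of equal rates stays valid, and chance imbalance is ordinary sampling error that the test already allows for. That stands. The added noise is also modest: the SE rises from 5.81 to 6.02–6.43 points, an increment of 0.2 to 0.6. Taken alone, pre-randomisation events give an arm difference with a standard deviation of √[2q(1 − q) / 100], or 2.4 to 4.2 points, but quoting that in isolation overstates what they add. All the rates are assumed, and no power was planned for this hypothesis.

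The remedy carries a risk of its own. Cystoscopy comes at the end of the case, so an injury may first be found after allocation with its onset uncertain, and bleeding can span both phases. A before/after judgement made once the arm is known could turn non-differential noise into differential classification. This also stands, and the fix has to deal with it.

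Two stronger readings are tempting but not supported. A reader might infer that dilution favours a finding that absorbable suture is no worse. The null as written runs the other way, and the protocol has no margin under which that effect could arise. A reader might also infer that the intra-operative record is completed by a surgeon who already knows the arm. The surgeon must know the suture once it is used, but the protocol does not say when the Surgical Procedures Form is completed or by whom, and it describes case report forms as recorded by research staff.

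**Conclusion.** The point holds as one of attenuation and lost precision. Followed as written, the plan counts events that the suture cannot have caused in its between-arm AE test. In the illustration, 3% to 10% of women with an earlier event costs about 5 to 15 percentage points of power at one-sided 0.05 (82% to 77–67%) and 3 to 11 at one-sided 0.10 (90% to 87–79%). These figures depend wholly on assumed AE rates, on counting women with any AE, and on independence of earlier and later events.

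A rise in false non-inferiority, 5.0% to 5.5–6.8% in the example, would arise only if a margin were set and absorbable suture were truly worse. The matter concerns an unpowered secondary hypothesis and leaves the primary outcome untouched. It is worth correcting because the correction is cheap and because onset relative to allocation is hard to reconstruct afterwards.

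**What to change.** For Secondary Outcome Measures item 3 and secondary hypothesis 3:

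1. Define the main comparison as AEs with onset after randomisation.
2. Log any intra-operative event already recognised before the REDCap allocation is opened, so that its classification is made without knowledge of the arm.
3. Count events first recognised after allocation, or of uncertain onset (for example, found at the end-of-case cystoscopy), as post-randomisation. Late effects of the hysterectomy that appear after allocation also stay in, which is consistent with intention to treat.
4. Tabulate pre-randomisation events by arm descriptively, and report the all-events comparison as a sensitivity analysis.
5. Keep sending all events to the data safety monitoring board.

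The cost is one form field, completed before allocation, and a few sentences in Statistical Methods. The AE form is not among the documents, so it may already record part of this. The compared AE rate will be lower than the total operative complication rate, which the descriptive table and the sensitivity analysis still show. Some events that truly began before allocation will remain in the main comparison under step 3. That is the price of a classification that does not depend on the arm.

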1. To compare the 1-year composite success rate (*leading edge of prolapse is at or above the hymen and apex has descended less than 1/3 of the vaginal length, no subjective feeling of bulge; no retreatment for pelvic organ prolapse (POP); no vaginal mesh/suture exposure*) of permanent versus delayed absorbable sutures for mesh graft attachment during robotic total hysterectomy and sacrocolpopexy.
2. To compare postoperative symptoms of pelvic floor disorders, including urinary incontinence, voiding dysfunction, pelvic organ prolapse, sexual dysfunction and quality of life between the 2 groups at 1 year.
3. To evaluate adverse outcomes in each group, classified according to the Clavien-Dindo system.

BACKGROUND

Symptomatic pelvic organ prolapse is common and 13%¹ to 19%^{2,3} of women undergo surgical repair. Reconstructive pelvic surgery is broadly divided into procedures that rely on existing native tissue versus the use of graft augmentation, either with synthetic or biologic materials. Native tissue vaginal repair, while associated with the lowest rate of surgical complications,⁴ has a high rate of recurrent prolapse. A recent randomized trial of uterosacral versus sacrospinous ligament fixation for POP demonstrated a 30% recurrence rate at 2 years.³

Abdominal sacrocolpopexy (SCP) is considered to be the most durable operation for advanced pelvic organ prolapse with reoperation rates of less than 5%.⁵⁻⁷ Minimally-invasive techniques of SCP, such as robotic-assistance, are associated with improved recovery times and less cost than abdominal SCP without a demonstrable difference in efficacy.^{8,9} While traditionally reserved for women with vaginal vault prolapse, SCP is increasingly considered as a primary surgical option for women who present with uterovaginal prolapse in an attempt to improve longer-term surgical outcomes. The optimal management of the uterus and cervix in these cases is unclear.

Rationale for total versus supracervical hysterectomy with concomitant SCP

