Participants may be approached for recruitment once they have decided to undergo surgical repair of symptomatic uterovaginal prolapse with hysterectomy and SCP and have undergone a standard history and physical examination, including a systematic evaluation of prolapse utilizing the pelvic organ prolapse quantification (POP-Q) system.²⁷ Participants will be screened against the inclusion and exclusion criteria, and if confirmed to meet all requirements will be eligible to be consented for enrollment into the study.

Participants will be considered enrolled in the study once the initial abdominal incision is made. All enrolled subjects will be considered part of the Intent-to-Treat (ITT) population for the final study analysis. All subjects enrolled who are treated with a study procedure will be considered part of the Per Protocol analysis.

The Screening & Enrollment Log will be completed by each site and emailed to the Project Manager on the first Monday of each month.

Study Withdrawal

Participants may withdraw consent at any point during the study. If a participant withdraws or is withdrawn, documentation will be made on an End of Study Form, including the reasons for withdrawal. There is no risk to participants who choose to withdraw from the study. Withdrawn study participants will be included in the Intent-to-Treat analysis and will not be replaced.

Pre-operative/Baseline Visit

The Pre-operative/Baseline Visit may occur up to 3 months prior to surgery. Once consented, subjects will be assigned a subject identification number that consists of a site letter (A-E) and a three-digit identification number.

At this visit participants will complete standardized and validated symptom bother (PFIQ-sf7), sexual functioning (PISQ-IR), and QoL questionnaire (PFDI-sf20) to assess baseline functioning. Preoperative urodynamic testing, imaging, anorectal manometry and/or cystourethroscopy may be completed at the discretion of the physician. Participants who do not meet the inclusion and exclusion criteria are considered screen failures. Information on screen failures will be captured within a case report form (CRF) and will include reasons for screen failure.

The Baseline Visit consists of the following:

- Informed Consent
- Participant Contact Form
- Inclusion/Exclusion Form
- Medical & Surgical History Form
- POP-Q Exam
- PFIQ-sf7, PISQ-IR, PFDI-sf20 questionnaires
- Assessment of pain and analgesic use

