Participant contact information will be reviewed at each follow-up visit. All efforts will be made by site staff to ensure minimal loss to follow-up of participants and will follow a site-specific loss to follow-up plan. This plan may include efforts such as telephone follow-up, Investigator-patient counseling, visit reminder tools, patient stipends, and/or other communication methods.

Week 6 Visit (-2 weeks/+4 weeks)

The primary outcome assessed at the Week 6 visit is evidence of suture or mesh exposure at the site of the sacrocolpopexy mesh. The POP-Q examination will be performed, as well as a vaginal examination (speculum and digital) to assess for suture or mesh exposure. In addition, pain and analgesic use and adverse events will be reviewed. All efforts will be made by site staff to ensure both follow-up anatomic measurements (POP-Qs) will be conducted by a healthcare provider other than the treating surgeon to reduce bias on outcomes after the study procedure. In the event the treating surgeon is the only qualified healthcare provider at the site trained in the POP-Q, the follow-up anatomic measurements will be conducted by the treating surgeon.

The Week 6 Visit consists of the following:

- Participant Contact Form update
- Assessment of pain and analgesic use
- Review of Adverse Events (if applicable)
- POP-Q Exam
- Vaginal examination (speculum and digital) to assess for suture or mesh exposure

Month 6 Phone Call (± 4 weeks)

Patients will be contacted by phone 6 months postoperatively to review contact information, pain and analgesic use, and adverse events.

The Month 6 Call consists of the following:

- Participant Contact Form update
- Assessment of pain and analgesic use
- Review of Adverse Events (if applicable)

Year 1 Visit (± 4 weeks)

The primary outcome assessed at the Year 1 visit is evidence of suture or mesh exposure at the site of the sacrocolpopexy mesh. The POP-Q examination will be performed, as well as a vaginal examination (speculum and digital) to assess for suture or mesh exposure. In addition, pain and analgesic use and adverse events will be reviewed. Participants will also complete the PFIQ-sf7, PISQ-IR, and PFDI-sf20. All efforts will be made by site staff to ensure both follow-up anatomic measurements (POP-Qs) will be conducted by a healthcare provider other than the treating surgeon to reduce bias on outcomes after the study procedure.

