In the event the treating surgeon is the only qualified healthcare provider at the site trained in the POP-Q, the follow-up anatomic measurements will be conducted by the treating surgeon. The End of Study form will also be completed by site staff.

The Year 1 Visit consists of the following:

- Assessment of pain and analgesic use
- Review of Adverse Events (if applicable)
- PFIQ-sf7, PISQ-IR, PFDI-sf20 questionnaires
- POP-Q Exam
- Vaginal examination (speculum and digital) to assess for suture or mesh exposure
- End of Study Form

[figure not shown]
All participants who have completed the study surgery will proceed to be followed through the above-outlined study visits to Year 1 where the primary endpoint analysis will be achieved when the last per protocol subject completes this visit. All participants completing the Year 1 visit will be considered to have completed the study.

The data collection schedule of the trial is depicted in Table 1. Flow through the trial is depicted in Figure 1.

Table 1. Data Collection Schedule

	Baseline Visit	Surgery (≤ 3 mo from BL Visit)	Week 6 Visit (-2 weeks/+4 weeks)	Month 6 Call (± 4 weeks)	Year 1 Visit (± 4 weeks)
Informed Consent	X				
Medical & Surgical History Form	X				
POP-Q Exam	X		X		X
Vaginal examination (speculum and digital)			X		X
PFIQ-sf7, PISQ-IR, PFDI-sf20 questionnaires	X				X
Assessment of pain and analgesic use	X		X	X	X
Contact information update			X	X	
Surgical Procedure Form		X			
Assessment of Adverse Events		X	X	X	X
End of Study Form					X

Figure 1. Trial Flow

This protocol will adhere to the CONSORT guidelines for performing and reporting randomized controlled trials.²⁸ Women who are eligible but decline enrollment will be characterized in a manner consistent with the CONSORT requirements.

STUDY POPULATION

Inclusion Criteria

The study will include women with symptomatic uterovaginal POP, who have completed childbearing, are seeking surgical management, and are willing to proceed with placement of abdominal mesh.

1. Age ≥ 18
2. Subject must have apical with anterior or posterior vaginal prolapse with leading edge of prolapse to or beyond the hymen ($C \geq - (TVL / 2)$ AND Ba or $Bp \geq 0$ by the POP-Q)
3. Subject reports a bothersome bulge they can see or feel per PFDI-20, question 3, response of 2 or higher (i.e., responses of "somewhat", "moderately", or "quite a bit")
4. Eligible for robotic or laparoscopic sacral colpopexy

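### The three questionnaires are scored at baseline and Year 1, but the arms are to be compared by t-test with no pre-specified baseline adjustment, which gives up precision on secondary outcomes

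*Combined protocol and SAP*

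**What the plan says.** The Pre-operative/Baseline Visit section schedules all three instruments: "At this visit participants will complete standardized and validated symptom bother (PFIQ-sf7), sexual functioning (PISQ-IR), and QoL questionnaire (PFDI-sf20) to assess baseline functioning". The Year 1 Visit section schedules them again: "Participants will also complete the PFIQ-sf7, PISQ-IR, and PFDI-sf20". Table 1 marks the same two time points. A baseline score may come from earlier routine care, within six months of surgery: "This includes previously performed POP-Q exams as well as previously collected questionnaires".

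The endpoint is described in two ways. Secondary Outcome Measures, item 2, speaks of change: "Assessment of participant changes in QoL, symptom bother, and sexual functioning at 1 year compared to baseline". Secondary Aim 2 is framed as a comparison of the two groups at 1 year and does not mention change: "To compare postoperative symptoms of pelvic floor disorders".

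On analysis, Statistical Methods says "Data analyses will include t-tests for continuous data", and later in the same sentence "multi-variable regression to assess the effects of any bivariate analyses found to have a positive relationship". No covariate is named there. Randomization is stratified by site, but no planned analysis of the questionnaires mentions site. No SD, correlation, target difference or power is given for any questionnaire score.

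**The concern.** When an outcome is measured before and after randomised treatment, the baseline value usually explains part of the variation in the later value. A t-test on the Year 1 score ignores that. A t-test on change uses the baseline but forces its coefficient to be 1, which is too large whenever the best-fitting slope is smaller. A linear model estimates the slope. It also adjusts for any chance baseline difference between the arms, which a Year 1 t-test leaves in place and a change score over- or under-corrects.

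At stake is the width of the intervals for symptoms, quality of life and sexual function. The trial was sized for mesh or suture exposure alone, so whatever precision these scores have must come from the number of women already planned and from the choice of analysis.

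**Working it through.** **Inputs from the documents.** Two measurements per woman for each instrument (Baseline and Year 1 Visit sections, Table 1). 1:1 randomisation stratified by site (Randomization, Sample Size). 80 evaluable women per arm, 200 in total after 20% loss (Sample Size).

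**The plan's own figure.** The only sample size concerns the binary primary outcome. With 10% against 1%, power 0.8, an uncorrected chi-square and z = 1.645 (alpha 0.1 two-sided, equivalently 0.05 one-sided):

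n = [1.645 × √(2 × 0.055 × 0.945) + 0.842 × √(0.0900 + 0.0099)]² / 0.09² = 78.3, so 79 per arm against 80 stated. Then 160 / (1 − 0.2) = 200. The figure reproduces on that reading of alpha. There is no corresponding figure for the questionnaires, so 80 per arm serves below only as an illustrative number.

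**Assumed, because the documents are silent.** The within-arm correlation r between baseline and Year 1 scores, and the ratio k = SD(Year 1) / SD(baseline).

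**Variances per woman, equal SDs (k = 1), in units of SD².**
- t-test on change: 2(1 − r)
- t-test on Year 1 score: 1
- model adjusting for baseline: 1 − r²

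Adjustment therefore removes 1 − (1 − r²) / [2(1 − r)] = (1 − r)/2 of the change-score variance, and r² of the Year 1 variance.

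| r | change | Year 1 | adjusted | removed vs change | removed vs Year 1 |
|---|---|---|---|---|---|
| 0.2 | 1.60 | 1 | 0.96 | 40% | 4% |
| 0.3 | 1.40 | 1 | 0.91 | 35% | 9% |
| 0.5 | 1.00 | 1 | 0.75 | 25% | 25% |
| 0.7 | 0.60 | 1 | 0.51 | 15% | 49% |
| 0.8 | 0.40 | 1 | 0.36 | 10% | 64% |

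The two losses run in opposite directions. A low r penalises the change score and a high r penalises the Year 1 score. Below r = 0.5, where 2(1 − r) exceeds 1, the change score does worse than ignoring baseline altogether.

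**Unequal SDs.** Against change, the share removed is 1 − k²(1 − r²) / (1 + k² − 2rk).
- k = 1.2, r = 0.3: 1 − 1.3104/1.72 = 24%. At r = 0.5: 1 − 1.08/1.24 = 13%.
- k = 0.85: 46% at r = 0.3 and 38% at r = 0.5.

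The share removed from a Year 1 t-test stays at r² whatever k is.

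**What this means at 80 per arm.** Assume equal SDs, two-sided 0.05 and 80% power; none of these is set by the plan for these scores. The detectable difference in SD units is (1.96 + 0.842) × √(2/80) = 0.443, times the square root of the variance above.
- r = 0.3: change 0.52, Year 1 0.44, adjusted 0.42
- r = 0.5: change 0.44, Year 1 0.44, adjusted 0.38
- r = 0.7: change 0.34, Year 1 0.44, adjusted 0.32

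Put as numbers of women, against a change-score t-test the adjusted analysis of 80 per arm is worth 80/0.65 = 123 per arm at r = 0.3 and 80/0.75 = 107 at r = 0.5. Against a Year 1 t-test it is worth 80/0.91 = 88 and 80/0.75 = 107.

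These are large-sample formulas. They ignore the few degrees of freedom spent on the baseline slope and on five sites, a minor cost at this size.

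**The case against.** The strongest defence is that nothing planned is wrong. Under randomisation both t-tests are valid and unbiased, so this is about efficiency and not error. That stands.

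Second, the methods sentence is not a closed list, and it does mention regression. A reader who stops at the t-test might infer that it is the only method planned for continuous data; the same sentence shows otherwise. The regression clause still does not supply the adjustment. It is triggered by a positive bivariate result, names no covariate and is silent on baseline scores. A real difference that the less precise t-test missed would not reach it.

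Third, a reader might infer that the plan t-tests change scores between arms. The documents never say so; that reading joins the outcome definition to a general sentence on methods. Secondary Aim 2 reads as naturally as a comparison of Year 1 scores, and the gain then is r² and not (1 − r)/2. It would also be too strong to say that baseline information is thrown away, since a change score uses it, though inefficiently.

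Fourth, Secondary Aim 2 does not rest on mean scores alone. Secondary Hypothesis 2 concerns a symptomatic success rate, subjective success is one PFDI-20 item, and pelvic floor symptoms are also collected as adverse events. No stated hypothesis concerns a mean questionnaire score. This limits the importance of the point, but the scores remain a listed secondary outcome that will be analysed.

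Finally, allowing baseline questionnaires from up to six months before surgery may lower r. That would shrink the gain over a Year 1 t-test and enlarge it over a change-score t-test. The score still precedes randomisation, so it remains a proper covariate.

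**Conclusion.** The point holds as a loss of precision on secondary outcomes. Baseline scores are scheduled for every woman, no baseline-adjusted comparison is specified, and on either reading of the endpoint a t-test is at best as precise as the adjusted model in large samples.

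The size is not known from the documents. With equal SDs it is about 10 to 40% of the variance of a change-score t-test for r from 0.8 down to 0.2, and 9 to 49% of the variance of a Year 1 t-test for r from 0.3 to 0.7. Unequal SDs move the first range: for example, 13 to 24% for r from 0.5 to 0.3 if the Year 1 SD is 1.2 times the baseline SD. A reader might settle on a single band of 25 to 35%. That needs r between 0.3 and 0.5, equal SDs and a change-score comparator, and the documents support none of these as fact.

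The binary primary outcome and the enrolment of 200 are unaffected. This is a worthwhile improvement, not a flaw that threatens the trial's main conclusion.

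**What to change.** In Statistical Methods, replace the t-test for the PFDI-20, PFIQ-7 and PISQ-IR scores with a pre-specified linear model, fitted whatever the bivariate results. The outcome is the Year 1 score; the terms are arm, the same instrument's baseline score, and site as the randomisation stratum. Report the adjusted mean difference between arms with its confidence interval. Keep the t-test for continuous variables that have no baseline value.

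The same sentence settles the difference between Secondary Aim 2 and Secondary Outcome Measures, item 2. With the baseline score in the model, taking change instead of the Year 1 score as the outcome lowers the baseline coefficient by 1 and leaves the arm effect and its interval the same. The text should still say which of the two is reported.

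The cost is a sentence or two in the analysis plan, with no new data, visits or participants.
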